10.5. Appendix 5: Abbreviations

Abbreviation/Term	Explanation
ADL	Activities of daily living
AE	Adverse event
ALP	Alkaline phosphatase
ALS	Amyotrophic lateral sclerosis
ALSAQ-40	Amyotrophic Lateral Sclerosis Assessment Questionnaire
ALSFRS-R	ALS Functional Rating Scale-Revised
ALT	Alanine aminotransferase
ANA	Anti-nuclear antibody
ANCOVA	Analysis of covariance
ANOVA	Analysis of variance
AST	Aspartate aminotransferase
BDI-FS	Beck Depression Inventory-Fast Screen
BID	Twice a day
BMI	Body mass index
CBC	Complete blood count
CFR	Code of Federal Regulations
CI	Confidence interval
CIOMS	Council for International Organizations of Medical Sciences
CK	Creatinine kinase
CKD-EPI	Chronic Kidney Disease Epidemiology Collaboration
CP	Conditional power
Cr	Creatinine
CRF	Case report form
CRO	Contract research organization
CTCAE	Common Terminology Criteria for Adverse Events
CYP	Cytochrome P450
CysC	Cystatin C
DILI	Drug induced liver injury
DMC	Data monitoring committee
DME	Durable medical equipment
EC	Executive Committee

Abbreviation/Term	Explanation
ECG	Electrocardiogram
ED	Early Discontinuation
eGFR	Estimated glomerular filtration rate
EQ-5D-5L	EuroQol-5D-5L
EQ-VAS	EuroQol Visual Analog Scale
FAS	Full analysis set
FSH	Follicle stimulating hormone
FSTA	Fast skeletal muscle troponin activator
FU	Follow-up
FVC	Forced vital capacity
GCP	Good Clinical Practice
HHD	Hand held dynamometry
HIPAA	Health Insurance Portability and Accountability Act
IB	Investigator's Brochure
ICF	Informed consent form
ICH	International Conference on Harmonisation
IEC	Independent ethics committee
IgG	Immunoglobulin G
IMP	Investigational medicinal product
INR	International normalized ratio
IP	Investigational product
IRB	Institutional review board
IUD	Intrauterine device
IUS	Intrauterine hormone-releasing system
IWRS	Interactive web response system
LAM	Lactational amenorrhoea method
LDH	Lactic acid dehydrogenase
LFT	Liver function test
LKM1	Liver Kidney Microsomal Antibody 1
LSM	Least square means
MAR	Missing at random
MCH	Mean corpuscular hemoglobin

Abbreviation/Term	Explanation
MCHC	Mean corpuscular hemoglobin concentration
MCV	Mean corpuscular volume
MedDRA	Medication Dictionary for Regulatory Activities
MiToS	Milano-Torino Staging
MMRM	Mixed Model for Repeated Measures
NIMP	Non-investigational medicinal product
NIV	Non-invasive ventilation
OCT	Organic cation transporter
OLE	Open Label Extension
PD	Pharmacodynamics
PK	Pharmacokinetics
PT	Preferred term
RBC	Red blood cell
RDW	Red cell distributions width
REB	Research Ethics Board
SAE	Serious adverse event
SAP	Statistical analysis plan
SC	Steering Committee
SD	Standard deviation
SGOT	Serum glutamic-oxaloacetic transaminase
SGPT	Serum glutamic-pyruvic transaminase
SoA	Schedule of activities
SOC	System organ class
SVC	Slow vital capacity
TBL	Total bilirubin
TDD	Total daily dose
TEAE	Treatment emergent adverse events
TSH	Thyroid stimulating hormone
ULN	Upper limit of normal
UPCR	Urine protein creatinine ratio
WBC	White blood cell
WHO	World Health Organization

Abbreviation/Term	Explanation
WOCBP	Women of childbearing potential

### TECHNICAL SUMMARY REPORT (TSR)

Name of Sponsor/Company Cytokinetics, Inc.	Individual Study Table Referring to Part of the Dossier: Volume:	(For National Authority Use Only):
Name of Finished Product: No generic or trade name assigned	Page:	
Name of Active Ingredient: Reldesemtiv (CK-2127107)		
Title of Study: A Phase 3, Multi-Center, Double-blind, Randomized, Placebo-Controlled Trial to Evaluate the Efficacy and Safety of Reldesemtiv in Patients with Amyotrophic Lateral Sclerosis (ALS)		
Investigators: Study Center(s): Patients will be enrolled from approximately 80 clinical trial sites, in the US, Canada, the United Kingdom, Ireland, France, Germany, Italy, Belgium, Portugal, Spain, Sweden, Poland, Switzerland, Australia, and the Netherlands.		
Studied period (years): 2021 to 2023	Phase of development: Phase 3	
Objectives and Endpoints:		
Objectives		Endpoint(s)
Primary		

 
To assess the effect of reldesemtiv versus placebo on functional outcomes in ALS
 
	
 
Change from baseline to Week 24 in ALSFRS-R total score
 
	
Secondary		

 
To assess the effect of reldesemtiv versus placebo on combined functional and survival outcomes in ALS
 
To assess the effect of reldesemtiv versus placebo on ventilatory function
 
To assess the effect of reldesemtiv versus placebo on quality of life
 
To assess the effect of reldesemtiv versus placebo on handgrip strength
 
	
 
Combined assessment of change in ALSFRS-R total score, time to dependence on assisted ventilation (use of non-invasive or invasive ventilation for <math>\geq 22</math> hours per day for <math>\geq 10</math> consecutive days), and survival time up to Week 24
 
Change from baseline to Week 24 in the percent predicted FVC
 
Change from baseline to Week 24 in the ALSAQ-40 total score
 
Change from baseline to Week 24 in handgrip strength (average of both hands)
 
	

**Methodology:**

This is a Phase 3, double-blind, randomized, placebo-controlled trial of reldesemtiv in patients aged 18 to 80 with ALS. The screening and qualification period for the trial will be no more than 21 days in duration. Approximately 555 eligible ALS patients will be randomized (2:1) to receive the following dose of reldesemtiv or placebo (stratified by riluzole use and edaravone use at baseline) for the first 24 weeks (double-blind placebo-controlled period):

- 300 mg reldesemtiv twice a day for a 600 mg total daily dose (TDD)
- Placebo twice daily

At the end of the 24-week double-blind, placebo-controlled period, patients will transition to the active drug period, where all patients will receive the following dose of reldesemtiv for the next 24 weeks:

- 300 mg reldesemtiv twice a day for a 600 mg TDD for patients who were not down titrated during the 24 weeks of blinded dosing
- 150 mg reldesemtiv twice a day for a 300 mg TDD for patients who were down titrated for any reason during the 24 weeks of blinded dosing

For the entire 48 weeks of dosing, patients and sites shall remain blinded to the randomized treatment assignment patients received during the first 24 weeks.

Study drug should be taken twice daily, morning and afternoon (at least 8 hours apart) and should be taken either with or within the 2-hour period following food.

For patients who complete Week 48 and want to enter the open label extension (OLE), they will not have the follow-up visit; instead, they will enter the OLE on the same day as their Week 48 visit. If the patient does not want to enter the OLE, or if the OLE has not yet been approved at the site, the follow-up visit will take place.

**Number of Subjects (planned and analyzed):** Approximately 740 patients will be screened in order to randomize/enroll approximately 555 patients, such that approximately 444 evaluable patients complete the 24-week of double-blind placebo-controlled period of the trial.

**Diagnosis and main criteria for inclusion:**

The key inclusion criteria are below. A full listing of eligibility criteria can be found in protocol Section 5.

- Males or Females between the ages of 18 and 80 years of age, inclusive, at screening.
- Diagnosis of familial or sporadic ALS (defined as meeting the laboratory-supported probable, probable, or definite criteria for ALS according to the World Federation of Neurology El Escorial criteria published in 2000 [Brooks 2000]). Patients who meet the possible criteria are eligible if they have lower motor neuron findings; those who have purely upper motor neuron findings are ineligible.
- First symptom of ALS  $\leq$  24 months prior to screening. The qualifying first symptoms of ALS are limited to manifestations of weakness in extremity, bulbar, or respiratory muscles. Cramps, fasciculations, or fatigue should not be taken in isolation as a first symptom of ALS.
- ALSFRS-R total score  $\leq$  44 at screening. Patients with a total score of 45 or higher may be rescreened  $60 \pm 7$  days following the original screening date and be deemed eligible if their ALSFRS-R total score is  $\leq$  44 or if their score is 2 or more points less than at initial screening. Such patients must continue to meet all other inclusion/exclusion criteria at the time of rescreening.
- Upright FVC  $\geq$  65.0% of predicted for age, height, sex, and race at screening according to Global Lung Initiative equation (Quanjer 2012).
- Able to perform reproducible pulmonary function tests defined as being able to perform FVC at screening with variability of the 2 highest raw values of less than 10% with a maximum of 5 trials permitted. Screening FVC results must be reviewed and approved by the central review process prior to randomization.
- Must be either on riluzole for  $\geq$  30 days prior to screening or have not taken it for at least 30 days prior to screening.
- Must have completed at least 2 cycles of edaravone at the time of screening or have not received it for at least 30 days prior to screening.
- Able to swallow whole tablets at the time of screening.
- Clinical laboratory findings within the normal range, or if outside the normal range, not deemed clinically significant by the Investigator, except as specifically indicated as laboratory exclusion.
- Must be either on the combination product (brand name only) of sodium phenylbutyrate and taurursodiol (also known as TUDCA, ursodoxicoltaurine or Tauroursodeoxycholic acid) for  $\geq$  51 days or have not received it for at least 30 days prior to screening

**Test product, dose and mode of administration:**

Reldesemtiv will be administered as 150 mg tablets, at a dose of 300 mg twice a day for a 600 mg TDD. Reldesemtiv tablets will be taken orally.

Patients must interrupt study drug for certain specified laboratory abnormalities. Hepatic related interruptions are permanent discontinuations. For renal related laboratory abnormalities, the interruption continues until the laboratory value in question has returned to the threshold specified in the protocol for re-initiation of treatment. Patients may then resume dosing at 1 tablet twice a day thereafter (150 mg twice daily). Patients also may be down-titrated to 1 tablet twice a day by the Investigator in the case of adverse events felt to be related to study drug. Once patients have been down-titrated to one tablet twice daily for any reason, their dose may not be returned to two tablets twice daily. A physician unblinded to renal laboratory results directs drug interruptions due to renal lab findings.

**Duration of treatment:**

The treatment period of the study is 48 weeks. Patients randomized to receive 300 mg reldesemtiv twice a day for a 600 mg TDD will receive reldesemtiv for the entire 48-week treatment period; patients randomized to receive placebo twice daily will receive placebo for the first 24 weeks and receive reldesemtiv for the next 24 weeks.

**Reference therapy, dose and mode of administration:**

Matching placebo will be administered as tablets, at a dose of 2 tablets twice a day. Matching placebo tablets will be taken orally.

In order to maintain the blind to site staff and the study operation team, a small portion of placebo patients will be randomly selected for down-titration to 1 tablet twice a day during the study by the CRO physician unblinded to the renal laboratory results.

**Criteria for evaluation (see protocol Section 3):**

Efficacy:

The primary efficacy endpoint is change from baseline to Week 24 in ALSFRS-R total score.

The secondary endpoints are as follows:

- Combined assessment of change in ALSFRS-R total score, time to dependence on assisted ventilation (either invasive or non-invasive), and survival time up to Week 24
- Change from baseline to Week 24 in the percent predicted FVC
- Change from baseline to Week 24 in the ALSAQ-40 total score
- Change from baseline to Week 24 in handgrip strength (average of both hands)

Safety:

Patient incidence of adverse events and serious adverse events.

**Statistical methods:**

Unless otherwise specified, efficacy analyses will be performed on the full analysis set (FAS) by randomized treatment group. The FAS consists of all randomized patients who receive any amount of study drug and have a baseline and at least one post baseline efficacy assessment or have survival status recorded during the 24-week double-blind placebo-controlled period.

The global null hypothesis for the primary endpoint is that there is no treatment difference in the change from baseline to Week 24 in ALSFRS-R total score between patients randomized to placebo and those randomized to reldesemtiv.

The primary analysis will be conducted using a Mixed Model for Repeated Measures (MMRM) with a restricted maximum likelihood method (SAS® PROC MIXED default). The model terms will include treatment group, baseline ALSFRS-R total score, visit, baseline riluzole use, and baseline edaravone use as well as the following interaction terms: baseline ALSFRS-R total score-by-visit and treatment group-by-visit interactions. Other baseline covariates identified by stepwise selection in a regression model will also be included in the primary analysis model if they are key predictor variables for the change from baseline to Week 24 in ALSFRS-R total score based on the blinded data. The regression model used to identify baseline covariates will include pre-study disease progression rate, age and baseline percent predicted FVC as model terms. An unstructured variance-covariance matrix will be used in the primary analysis model.

Prior to applying the MMRM, missing data will be imputed using the multiple imputation procedure (Rubin 1987) for the primary analysis, and the estimates from each imputed dataset will be combined into one set of overall estimates using the SAS® PROC MIANALYZE procedure. The extent of missing data and the pattern of missing data reasons will be tabulated. Least square means (LSM), LSM difference and the corresponding standard errors, 95% confidence intervals (CI) and p-values will be presented. Multiplicity will be addressed using closed testing procedure detailed in [Section 8.5](#).

Safety data will be summarized using descriptive statistics for the safety analysis set that consists of patients who take at least one dose of study drug. All AE terms will be coded using the Medical Dictionary for Regulatory Activities (MedDRA). Primary system organ class (SOC) and preferred term (PT) of the TEAEs will be tabulated by the early-start and delayed-start treatment groups and by the study periods (double-blind placebo-controlled period and active drug period). TEAEs will also be summarized by severity and relationship to study drug. AEs that led to early discontinuation from treatment or trial will be summarized.

## 1. LIST OF ABBREVIATIONS

Abbreviation	Term
AE	Adverse Event
ALP	Alkaline Phosphatase
ALT	Alanine Aminotransferase
ALS	Amyotrophic Lateral Sclerosis
ALSAQ-40	Amyotrophic Lateral Sclerosis Assessment Questionnaire
ALSFRS-R	Amyotrophic Lateral Sclerosis Functional Rating Scale-Revised
ALT	Alanine Aminotransferase
ANCOVA	Analysis of Covariance
AST	Aspartate Aminotransferase
AUC	Area under the ROC Curve
BDI-FS	Beck Depression Inventory (BDI®) - Fast Screen
CI	Confidence Interval
CP	Conditional Power
CYP3A4	Cytochrome P450 Family 3 Subfamily A Member 4
eCRF	Electronic Case Report Form
CRO	Contract Research Organization
CSR	Clinical Study Report
DMC	Data Monitoring Committee
DME	Durable Medical Equipment
EC	Ethics Committee
ECG	Electrocardiogram
EQ-VAS	EuroQol - Visual Analogue Scale
FAS	Full Analysis Set
FVC	Force Vital Capacity
HHD	Hand Held Dynamometry
ICH	International Council for Harmonisation
IRB	Institutional Review Board
LLN	Lower Limit of Normal
LSM	Least Squares Mean
MAR	Missing At Random
MedDRA	Medical Dictionary for Regulatory Activities Terminology

Abbreviation	Term
MiToS	Milano-Torino Staging
MMRM	Mixed Model for Repeated Measures
MNAR	Missing Not At Random
NIV	Non-Invasive Ventilation
OCT1	Organic Cation Transporter 1
OLE	Open Label Extension
PCS	Potential Clinical Significance
PK	Pharmacokinetics
PT	Preferred Term
REB	Research Ethics Board
SAE	Serious Adverse Event
SAP	Statistical Analysis Plan
SAS	Statistical Analysis System (SAS ® )
SOC	System Organ Class
TDD	Total Daily Dose
TEAE	Treatment-Emergent Adverse Event
TESAE	Treatment-Emergent Serious Adverse Event
ULN	Upper Limit of Normal
VAS	Visual Analogue Scale
WHO	World Health Organization

## **2. INTRODUCTION**

The purpose of this statistical analysis plan (SAP) is to provide a technical elaboration of the planned analyses and detailed data displays to be included in the Clinical Study Report (CSR) for CY 5031 study.

This SAP was developed in accordance with ICH E9 and ICH E9 (R1) guideline. All decisions regarding final analysis, as defined in this SAP document, will be made prior to the study database lock. Further study information can be found in the protocol.

### **3. STUDY OBJECTIVES AND ENDPOINTS**

#### **3.1. Study Objectives**

##### **3.1.1. Primary Objective**

The primary objective of the study is to assess the effect of reldesemtiv versus placebo on functional outcomes in ALS.

##### **3.1.2. Secondary Objective**

The secondary objectives of the study are listed as follows:

- To assess the effect of reldesemtiv versus placebo on combined functional and survival outcomes in ALS
- To assess the effect of reldesemtiv versus placebo on ventilatory function
- To assess the effect of reldesemtiv versus placebo on quality of life
- To assess the effect of reldesemtiv versus placebo on handgrip strength

#### **3.2. Study Endpoints**

##### **3.2.1. Primary Endpoints**

The primary endpoint of the study is change from baseline to Week 24 in ALSFRS-R total score.

##### **3.2.2. Secondary Endpoints**

- Combined assessment of change in ALSFRS-R total score, time to dependence on assisted ventilation and survival time up to Week 24. Dependence on assisted ventilation is defined as using non-invasive or invasive ventilation for  $\geq 22$  hours per day for  $\geq 10$  consecutive days.
- Change from baseline to Week 24 in the percent predicted forced vital capacity (FVC)
- Change from baseline to Week 24 in the ALSAQ-40 total score
- Change from baseline to Week 24 in handgrip strength (average of both hands)

## 4. STUDY DESIGN

### 4.1. Summary of Study Design

This is a Phase 3, double-blind, randomized, placebo-controlled trial of reldesemtiv in patients aged 18 to 80 with ALS. The screening and qualification period for the trial will be no more than 21 days in duration. Approximately 555 eligible ALS patients will be randomized (2:1) to receive the following dose of reldesemtiv or placebo (stratified by riluzole use at baseline and edaravone use at baseline) for the first 24 weeks (double-blind placebo-controlled period):

- 300 mg reldesemtiv twice a day for a 600 mg total daily dose (TDD)
- Placebo twice daily

At the end of the 24-week double-blind, placebo-controlled period, patients will transition to the active drug period, where all patients will receive the following dose of reldesemtiv for the next 24 weeks:

- 300 mg reldesemtiv twice a day for a 600 mg TDD for patients who were not down titrated during the 24 weeks of blinded dosing
- 150 mg reldesemtiv twice a day for a 300 mg TDD for patients who were down titrated during the 24 weeks of blinded dosing

For the entire 48 weeks of dosing, patients, sites, Sponsor personnel and their contractors employed to work in any way on the conduct of the trial (with the exception of the unblinded medical monitor) shall remain blinded to the randomized treatment assignment for the first 24 weeks.

Study drug should be taken twice daily, morning and afternoon (at least 8 hours apart) and should be taken either with food or within a 2-hour period following food.

For patients who complete Week 48 and want to enter the open label extension (OLE), they will not have the follow-up visit; instead, they will enter the OLE on the same day as their Week 48 visit. If the patient does not want to enter the OLE, or if the OLE has not yet been approved at the site, the follow-up visit will take place.

### 4.2. Definition of Study Drugs

This section describes any study drug: investigational product (IP) (ie, reldesemtiv) or placebo intended to be administered to a trial patient according to the protocol.

Arm Name	Active	Placebo
IP/Product Name	Reldesemtiv	Placebo
Type	Drug	Drug
Dose Formulation	Tablet	Tablet
Unit Dose Strength(s)	150 mg	Matching placebo
Dosage Level(s)	2 tablets twice a day for 600 mg TDD	2 matching placebo tablets twice a day
Route of Administration	Oral	Oral
Use	Experimental	Placebo
IMP and NIMP	IMP	IMP

Arm Name	Active	Placebo
Sourcing	Patheon, Inc. Toronto Regional Operations (TRO) [name]	Patheon, Inc. Toronto Regional Operations (TRO) [name]
Packaging and Labeling	IP will be provided in bottles. Each bottle will be labeled as required per country requirement	Placebo will be provided in bottles. Each bottle will be labeled as required per country requirement

### 4.3. Sample Size Considerations

#### 4.3.1. Sample Size Justifications

With a 2:1 randomization ratio to reldesemtiv and placebo groups, respectively, an initial sample size of approximately 555 patients is required to achieve at least 90% power to detect a 1.8 point treatment difference between reldesemtiv and placebo in the change from baseline to Week 24 in ALSFRS-R total score. This calculation is based on a two-sample t-test with two-sided alpha at 0.05 level, a common standard deviation of 5.5 points, and accounting for data missing and early treatment termination.

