9.2. Sample Size Determination

With a 2:1 randomization ratio to reldesemtiv and placebo groups, respectively, a sample size of approximately 555 patients is required to achieve at least 90% power to detect a 1.8 point treatment difference between reldesemtiv and placebo in the change from baseline to Week 24 in ALSFRS-R total score. This calculation is based on a two-sample t-test with two-sided alpha at 0.05 level, a common standard deviation (SD) of 5.5 points, and accounting for missing data and early treatment termination.

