9.5. Interim Analyses

Two interim analyses are planned for this trial. The interim analysis methods and the specifications of the data snapshots will be detailed in an interim analysis plan.

Twelve (12) weeks after approximately one-third or more of the planned sample size is randomized, the first interim analysis may be triggered. Its purpose is to determine if there is a lack of effect of reldesemtiv on the ALSFRS-R in CY 5031, a finding that would be inconsistent with the prior observed effect on the change from baseline at 12 weeks in ALSFRS-R total score in the Phase 2 trial, CY 5022. At this interim analysis, the Data Monitoring Committee (DMC) will receive unblinded efficacy data from the independent, third-party biostatistical group supporting them and assess the effect of reldesemtiv on the change from baseline to Week 12 in the ALSFRS-R total score. At this interim assessment, if the treatment difference for change from baseline to Week 12 in ALSFRS-R total score has a one-sided p-value larger than or equal to 0.5 (ie, the estimated treatment difference of the change from baseline at Week 12 in ALSFRS-R total score is favoring placebo), the DMC may recommend stopping the trial due to futility. This futility analysis based on the data of change from baseline to Week 12 in ALSFRS-R will not have any alpha spending. The Sponsor will monitor the blinded aggregate standard deviation of the change from baseline to Week 12 in ALSFRS-R total score periodically and possibly adjust the specified alpha before this interim analysis is conducted.

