#### 4.3.2. Sample Size Re-estimation

The sample size will not be re-estimated based on the results of the 1st interim analysis.

The 2nd interim analysis will be triggered 24 weeks after at least one-third of patients required to be enrolled are randomized, and will be based on the data from all patients who are expected to complete 24 weeks of treatment. The sample size may be re-estimated based on the 2nd interim analysis results being reviewed by the DMC. For the primary endpoint, if futility criterion is not met (see [Section 5.1](#) for the futility criterion) and the conditional power under the current trend at the time of the interim look is within the pre-specified promising zone from 0.40 to 0.90, the DMC may recommend increasing the sample size by a pre-specified fixed number of 150 to ensure sufficient power. This method is referred to as the CDL adaptive method and was initially proposed by Chen, DeMets, and Lan (2004) as later extended by Gao, Ware and Mehta (2008) and Mehta and Pocock (2011) ([Chen 2004](#); [Gao 2008](#); [Mehta 2011](#), respectively). It is used to control type-1 error for sample size increase based on unblinded interim data. Within the pre-specified promising zone and a pre-specified fixed increase of the sample size, the CDL method could allow the final analysis to include all data before and after the interim look without inflating the type-1 error.

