Twenty-four (24) weeks after at least one-third of the planned sample size is randomized; the second interim analysis will be triggered. The safety analysis will include all data points collected from available patients at the time of the interim data review. The efficacy analysis will include patients who would be expected to complete 24 weeks of the study by the time of data cut off for the second interim data review, i.e., those who complete 24 weeks of the study and those who are expected to complete 24 weeks of the study but early terminate prior to Week 24. Those patients who have not had the opportunity to reach Week 24 by the time of the data cutoff will not be included in the second interim efficacy analysis. The goal of the second interim analysis is to evaluate whether the proposed Phase 3 trial has adequate power to achieve a statistically significant effect on the primary endpoint in the final primary analysis, given the planned enrollment, or if continuing the trial is futile. At this interim analysis, the DMC will receive unblinded efficacy data from the independent, third-party biostatistical group supporting them and assess the effect of reldesemtiv on the primary endpoint. In terms of futility, the DMC may recommend stopping the trial if the conditional power (CP) under the current trend is less than 0.10 for the primary endpoint. The futility boundary is non-binding. The DMC is to make a recommendation to stop the trial using their collective judgment and the totality of evidence available. The DMC may consider the first secondary endpoint in a similar fashion.

If the CP of primary endpoint is within a pre-specified promising zone from 0.40 to 0.90, the DMC may recommend increasing the sample size by a pre-specified fixed number of 150 unless there is any safety concern or other concerns that preclude the recommendation. This method is referred to as the CDL adaptive method and was initially proposed by Chen, DeMets, and Lan, later extended by Gao, Ware and Mehta, and Mehta and Pocock ([Chen 2004](#); [Gao 2008](#); [Mehta 2011](#), respectively). It is used to control type-1 error for sample size increase based on unblinded interim data. Within the pre-specified promising zone and a pre-specified fixed increase of the

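### The stated 90% power is a fixed-sample figure that leaves out the futility looks; if the second-interim rule is followed, power is about 85–89%, depending on when the look falls and whether the 150-patient increase is used

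*SAP*

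**What the plan says.** SAP 4.3.1 states that "an initial sample size of approximately 555 patients is required to achieve at least 90% power to detect a 1.8 point treatment difference", and gives the basis: "This calculation is based on a two-sample t-test with two-sided alpha at 0.05 level, a common standard deviation of 5.5 points". Allocation is 2:1. The text also allows for missing data and early termination of treatment, and the SAP technical summary gives the resulting target: "approximately 444 evaluable patients complete the 24-week of double-blind placebo-controlled period". Protocol 9.2 repeats the claim: "a sample size of approximately 555 patients is required to achieve at least 90% power to detect a 1.8 point treatment difference". None of these places mentions an interim analysis.

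Two futility looks are described elsewhere.

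- **First look** (protocol 9.5, SAP 5.1). It may be held 12 weeks after about one-third or more of the patients are randomized. The DMC may recommend stopping if the Week 12 ALSFRS-R comparison "has a one-sided p-value larger than or equal to 0.5".
- **Second look** (SAP 5.1). It is held 24 weeks after at least one-third are randomized. "In terms of futility, the DMC may recommend stopping the trial if the conditional power (CP) under the current trend is less than 0.10". This boundary is declared non-binding and left to the DMC's judgment.

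If conditional power lies between 0.40 and 0.90 at the second look, SAP 4.3.2 lets the DMC recommend "increasing the sample size by a pre-specified fixed number of 150 to ensure sufficient power". Neither document gives a stopping probability or a power figure with the looks included. Interim methods are deferred to a separate interim analysis plan.

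**The concern.** A non-binding futility boundary leaves the type I error intact, but it does not leave power intact. Each time a rule stops a trial that would have succeeded, power is lost. With no margin in the fixed-sample figure, any futility rule that is followed takes power below 90% unless something offsets the loss.

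A reader of SAP 4.3.1 or protocol 9.2 would take 90% as the chance that this trial succeeds if the drug works as planned. The plan does not say how far that chance falls when its own stopping criteria are applied, or how much of the loss the sample size increase recovers.

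**Working it through.** **1. Reproduce the plan's figure.** Inputs from SAP 4.3.1 and the technical summary: difference 1.8, SD 5.5, 2:1, 444 evaluable (296:148).

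- SE = 5.5 × √(1/296 + 1/148) = 0.554. Drift = 1.8/0.554 = 3.251.
- Exact noncentral-t power = 90.04% at two-sided 0.05, and 90.02% at the final level of 0.0499. The normal approximation at 0.0499, used below, gives 90.15%.
- 444/0.80 = 555. The plan's figure is confirmed.

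**2. Second-look boundary at information fraction t = 1/3.** With final critical value c = 1.9608, conditional power under the current trend is Φ[(Z/√t − c)/√(1 − t)]. Setting this to 0.10:

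- Z = √t × [c − 1.2816 × √(1 − t)] = 0.5774 × (1.9608 − 1.0464) = 0.528.
- Interim SE = 0.554 × √3 = 0.959, so the rule is met when the observed difference is below 0.528 × 0.959 = 0.51 points.
- At that boundary, conditional power under the design effect of 1.8 is Φ[(0.528 × 0.5774 + 3.251 × 2/3 − 1.9608)/0.8165] = 73%.

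**3. Cost under a true 1.8-point difference.**

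- The mean of Z at the look is 3.251 × 0.5774 = 1.877, so P(stop) = Φ(0.528 − 1.877) = 8.9%.
- Not all of these trials would have succeeded. Integrating the probability of a stop in a trial that would have rejected at the end gives 5.45 points.
- Power = 90.15 − 5.45 = 84.7%.

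**4. Add the sample size increase.** 150 randomized × 444/555 = 120 evaluable. The increase is applied whenever conditional power is 0.40–0.90, with the conventional final test.

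| Information at second look | P(futility stop) | Power, rule followed | With +150 |
|---|---|---|---|
| 1/3 | 8.9% | 84.7% | 86.3% |
| 0.4 | 7.4% | 86.1% | 87.7% |
| 0.5 | 6.0% | 87.5% | 89.2% |
| 0.6 | 5.2% | 88.4% | 90.2% |

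The increase returns 1.6 points at one-third information and about 1.8 at the later looks.

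**5. Add the Week 12 rule at one-third information.** This needs inputs that the documents do not supply for this trial. Protocol 4.2 gives a Week 12 difference of 0.9 points from the Phase 2 trial (pooled doses, whole population). I assume 0.9 or 1.2, a Week 12 SD of 3.0–4.0 and a Week 12/Week 24 correlation of 0.7. Power is by simulation.

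| Week 12 effect, SD (assumed) | P(stop at first look) | Both rules | With +150 |
|---|---|---|---|
| 0.9, 3.0 | 4.3% | 83.2% | 84.7% |
| 0.9, 3.5 | 7.0% | 81.7% | 83.2% |
| 0.9, 4.0 | 9.8% | 79.9% | 81.4% |
| 1.2, 3.0 | 1.1% | 84.5% | 86.0% |
| 1.2, 3.5 | 2.5% | 84.0% | 85.5% |
| 1.2, 4.0 | 4.3% | 83.1% | 84.7% |

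The span is roughly 80–86%. At half information with the 0.9 effect, both rules with the increase give 86.4–88.6%.

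**6. Sensitivity to effective sample size.** If the information exceeds 444 completers (assumed values), the second rule alone at one-third information gives 88.3% at 500 and 91.0% at 555.

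**The case against.** The best defence has four parts.

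- **The 90% is calculated correctly.** This stands. A reader might infer that the sample size arithmetic is wrong. It is not: the text describes a t-test, the result reproduces, and SAP 4.3.1 calls 555 an initial size. What is missing is an operating characteristic.
- **The rules do not compel a stop.** This stands. Both say the DMC may recommend stopping, the second is explicitly non-binding, the first look is itself optional, and its cut-off may be adjusted beforehand. The loss is therefore conditional on the rules being followed. That is a reason to state the condition, not to omit the cost.
- **One-third is a minimum, and 444 may understate the information.** Both points stand. A later look costs less. The primary analysis (SAP 8.6.1) uses the full analysis set, multiple imputation and covariate adjustment, so partial data may add information. The documents do not quantify this, and an effective size of 555 would mean that dropout cost nothing.
- **Futility rules are meant to give up some power.** This also stands. At one-third information the second rule stops about 70% of trials with no effect (Φ(0.528) = 0.70), so I propose no change to the boundary.

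A reader might also infer that the design delivers one fixed figure such as 83%. The documents do not support that, because it needs a Week 12 effect, SD and correlation that they do not give for this trial. Nor do they show what power figure the DMC was given: the interim analysis plan and DMC charter are separate documents.

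**Conclusion.** The point holds as a gap in the stated operating characteristics. The 90% is valid only if no futility stop is made. With 444 evaluable patients, and the second-interim criterion followed at one-third information, a true 1.8-point effect is stopped for futility 8.9% of the time. Power is then about 85%, or about 86% with the increase. At half information it is 87.5%, or 89% with the increase. These figures need no input beyond the plan's own, apart from the timing of the look, the rule being followed and, for the increase, the same 20% loss among the added patients.

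The both-rules figure, roughly 80–86% at one-third information, rests on assumed Week 12 inputs and should be read only as a range. The loss shrinks with a later look, a larger effective sample size or a DMC that does not apply the criteria mechanically. Describing the increase as ensuring sufficient power overstates a gain of about 1.6 points at one-third information.

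**What to change.** In SAP 4.3.1, protocol 9.2 and the protocol synopsis:

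- Label the 90% as fixed-sample power with no futility stop.
- Beside it, state the futility-stop probability under a 1.8-point difference and the overall power when the second-interim rule is followed, with the 150-patient increase included: 8.9% and about 86% at one-third information; 6.0% and about 89% at half.
- Give power with both rules followed as a range, and state the Week 12 effect, SD and Week 12/Week 24 correlation behind it. Do not insert a single figure.
- Say that these values apply so far as the DMC follows the criteria, and state the effective sample size assumed.

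In SAP 4.3.2, replace the statement that the increase ensures sufficient power with its actual effect, about 1.6 points of overall power at one-third information.

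The cost is wording and a short calculation or simulation. The stated power becomes less favourable. No patients are added, and neither the boundary nor the final test changes.
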